9.2 Safety Parameters

9.2.1 Safety Parameters

Safety parameters will include all AEs reported for each group, radiographic stability at each postoperative visit and revision rates.

9.2.2 Safety Analysis

All AEs will be listed, tabulated and summarized by event, number and percent of cases/subjects. AE rates and 95% confidence intervals will be presented. In addition, a

CONFIDENTIAL

Fisher's exact test will be used to compare the AE rates between the Rejuvenate® Modular Hip System and the Secur-Fit™ HA groups or cohorts, if appropriate.

For categorical variables, such as radiographic stability, the number and percent in each category will be presented.

9.3 *Missing Data*

No missing data will be imputed for the primary analysis and secondary analyses.

9.4 *Statistical Methodology*

9.4.1 *Data Summary*

The following is a detailed proposal of statistical analyses planned for data collected during the study.

Descriptive statistics will be computed for all preoperative conditions and demographic parameters. That is, for continuous data (e.g. HHS) the N, mean, median, standard deviation, minimum and maximum will be computed. For categorical data (e.g. gender) the frequency will be computed. If appropriate, the data will be presented by the Rejuvenate® Modular Hip System and the Secur-Fit™ HA groups.

Descriptive statistics and statistical comparisons for important demographic, efficacy and safety variables will be provided in tables.

A survival analysis for revision/removal of the modular femoral stem/neck construct will be performed.

9.4.2 *Sample Size Calculation*

Given an estimated revision rate for both groups at 2.5% and a non-inferiority margin of 5%, with a one-sided alpha of 0.05 and 80% power, a total of 147 cases per group are required to reject the null hypothesis that the revision rate for Rejuvenate® Modular Hip System cases is 5% greater than for Secur-Fit™ HA monolithic femoral stem cases. In order to control for a 20% drop-out rate, 183 cases per group are required.

CONFIDENTIAL

A total of 240 cases received the Secur-Fit™ HA femoral stem in the Trident® X3® Polyethylene Insert Study, a historical control. Therefore, although only 183 cases are needed for statistical power, 240 cases will be enrolled in the Rejuvenate® Modular Hip System Outcomes Study.

9.4.3 Interim Analyses and early Stopping Considerations

No interim analysis is planned.

9.4.4 Patient Populations

Modified Intent-to-Treat (ITT) Population: The study population for analysis will include all subjects who receive the Rejuvenate® Modular Hip System or the Secur-Fit™ HA monolithic femoral stem. This does not include cases censored from analysis for a reason that may have a significant impact on outcome.

The primary and secondary efficacy analyses will be based on the per protocol population.

Per Protocol Population: The study population will include all subjects who receive the Rejuvenate® Modular Hip System or the Secur-Fit™ HA monolithic femoral stem. This does not include cases that have major protocol violations including the violation of entry criteria. In order for cases to be included in the per protocol population, the data required for analysis of a specific parameter must be present. Any data of secondary variables will be included, where possible.

The primary efficacy analyses and safety analysis will be based on the modified ITT population; the secondary efficacy analyses will be based on the per protocol population.

10 Study Procedures

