10.3 Early Withdrawal of Subjects

When and How to Withdraw Subjects

In the event that the subject is discontinued by the investigative center prior to the final study evaluation, the subject will be notified by the center that he/she is no longer in the study and a Study Termination CRF will be completed.

The following is a list of reasons for which subjects may be withdrawn and the date of termination that should be used on the Study Termination CRF in each situation. This list is not all inclusive:

Termination Reason	Date of Termination
Death	Date of death
Investigative center termination	Date of study close-out visit
Lost to follow-up	Date Stryker termination approval given
Voluntary withdrawal	Date subject notified center of withdrawal
Revision/removal of study device	Date of revision/removal procedure
Study device not implanted	Date of surgery
Surgery not performed	Date Stryker termination approval given

At the time of study surgery it is required that the following components are implanted:

- Rejuvenate® Modular Stem
- Rejuvenate® Modular Neck
- Stryker Trident® or Tritanium™ Primary acetabular shells, with or without screw fixation, as well as Stryker Restoration® ADM acetabular shells
- Stryker alumina ceramic inserts (for use with Trident® acetabular shells) or X3® inserts
- Stryker LFIT™ CoCr heads; delta ceramic heads; or alumina ceramic heads with adapter sleeve

Revision or removal of the Rejuvenate® Modular stem/neck construct constitutes a failure and study termination for the subject.

CONFIDENTIAL

If acetabular insert or femoral head exchange is required during the study, the event is considered a reoperation and does not constitute a failure or study termination.

If acetabular shell and insert revision is required during the study, the event is considered a reoperation and does not constitute a failure or study termination.

If the subject fails to return for his/her follow-up appointments, every effort should be made to contact the subject to assess his/her health status. If after attempting to contact the subject through three documented phone calls and a certified letter, the subject still does not respond, he/she will be considered lost to follow-up. A Study Termination CRF will be completed only after notifying Stryker of the subject's status and being given approval to terminate.

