Intraoperative fissure, fracture, or perforation of the femur, acetabulum or trochanter can occur due to impaction of the component into the prepared femoral canal or acetabulum. Postoperative femoral or acetabular fracture can occur due to trauma, the presence of defects or poor bone stock.

If bone screws are used, appropriate selection of bone screw length and location is essential to avoid damage to underlying soft tissue structures. Perforation of the pelvic wall can result in internal bleeding and possible damage to vital organs.

Metal sensitivity reactions have been reported following joint replacement.

AEs may necessitate reoperation, revision, arthrodesis of the involved joint, girdlestone or amputation of the limb.

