*Data from the following Stryker sponsored clinical studies was used as a basis for this table: Omnifit® HA, ABC/Trident®, Meridian®, Citation®, Secur-Fit™, Accolade® TMZF and Trident® X3®. There were 2,966 total cases (hips) in 2,697 subjects after combining results from these seven studies. Percentages for operative and device related events were calculated by dividing the number of cases with one or more reported event by the number of cases (hips) enrolled. Systemic events were calculated by dividing the number of subjects with one or more reported events by the number of subjects enrolled. The protocols for the Omnifit® HA and ABC/Trident® studies originally required that all AEs be reported; however, after these products became commercially available, the protocols were modified and required that only operative related events be reported. For the ABC/Trident®, this change occurred in February 2003 and for the Omnifit® HA, in December 1990. The protocol for the Trident® X3® and Accolade® TMZF studies required that operative site AEs and any event meeting the definition of a serious event be reported. The protocols for Secur-Fit™, Citation® and Meridian® required that all AEs were reported. Percentages for primary THR taken from published literature represent averages or ranges as noted.

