I. DEVIATION INFORMATION

(Report One Deviation per form)

A. TYPE OF DEVIATION (Check one)

 Informed Consent: (Check one)

- Study procedures performed prior to informed consent
- Incorrect informed consent version used
- Other (Specify) _____

 Inclusion / Exclusion: Subject enrolled does not meet the inclusion / exclusion criteria **Treatment:** Protocol specified study component(s) not implanted (Check all that apply)

 Acetabular Shell	 Acetabular Insert	 Femoral Bearing Head
 Modular Neck / Modular Stem*	 Other (Specify) _____	

*(Complete Study Termination form)

 Evaluation(s): (Specify one visit below)

VISIT: Pre-Op 6 Week 1 Year 2 Year 3 Year 4 Year 5 Year 6 Year 7 Year 8 Year 9 Year 10 Year

(Specify one selection)

- Missed entire visit
- Deviation in visit (Check all that apply and specify)
 - Required form(s)/X-ray(s) not done
 - Evaluation(s) occurred outside of protocol specified time window
 - X-ray Unevaluable (i.e. unreadable/poor quality)

(If Deviation in visit, specify each form/X-ray)

- Biomechanical Measurement
- Follow-up Questionnaire
- Functional Evaluation
- SF-12
- LEAS
- X-ray - A/P Pelvis
- X-ray - A/P Femur
- X-ray - Lateral

 Other: (Specify) _____

B. Briefly describe the deviation and why this occurred. _____

INVESTIGATOR NAME (PRINT):

INVESTIGATOR SIGNATURE:

DATE:

--	--

 /

--	--	--

 /

--	--	--

D D M M M Y Y Y Y

Stamp Date Received:

INITIAL/DATE:

Receipt _____

Entry _____

Verification _____

Monitored _____

For Stryker Use Only

[name]

SUBJECT ID: **6 8**
 Study # Site # Subject #**GENERAL INFORMATION**SUBJECT INITIALS:
(If there is no middle initial please use "-")OPERATIVE SIDE: (use one form per side)
 Right LeftTERMINATION DATE: / /
D D M M M Y Y Y Y**I. STUDY TERMINATION****A. DID SUBJECT COMPLETE STUDY ACCORDING TO PROTOCOL?** Yes No*

* If No, answer questions B and C

B. CHECK ONE PRIMARY REASON BELOW:

- Death (Complete AE form)
- Investigative Site Terminated
- Lost To Follow-Up

List efforts to contact subject:

1st phone call:

	

	

	

2nd phone call:

3rd phone call:

Certified letter sent:

Additional efforts:

- Revision/Removal of Study Device (Complete AE form)

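### The only safety set is limited to subjects who receive the stem, so a case abandoned because of an intraoperative complication drops out of the adverse event rates

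*Combined protocol and SAP*

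**What the plan says.** Section 9.4.4 assigns the safety analysis in these words: "The primary efficacy analyses and safety analysis will be based on the modified ITT population". It defines that population as follows: "The study population for analysis will include all subjects who receive the Rejuvenate® Modular Hip System or the Secur-Fit™ HA monolithic femoral stem". A further clause narrows it without giving criteria: "This does not include cases censored from analysis for a reason that may have a significant impact on outcome". The per protocol population is also restricted to recipients. No set of all enrolled or all attempted cases is defined, and *receive* is not explained.

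The protocol foresees operations in which the stem is not implanted. Section 10.3 lists "Study device not implanted" among the reasons for which a subject may be withdrawn, with the date of surgery as the termination date. On the deviation form in Appendix F, the entry for a modular neck or stem that was not implanted carries the instruction "Complete Study Termination form".

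Section 12.2 names the relevant complication: "Intraoperative fissure, fracture, or perforation of the femur, acetabulum or trochanter can occur due to impaction of the component".

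Other sections collect and promise to report such events. Section 8.1 makes protocol-defined adverse events reportable from consent. The Surgical Details form asks about intraoperative complications and sends a positive answer to an adverse event form. Section 2.2 undertakes to collect operative site events and compare them with the control and with published data. Section 9.2.2 undertakes to list and tabulate all adverse events and to give rates with 95% confidence intervals.

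**The concern.** Suppose the femur cracks while the stem is being impacted and the surgeon finishes the operation with another stem. The patient was consented, enrolled and operated on with the intention of implanting the Rejuvenate system. On the plain reading of Section 9.4.4 the patient did not receive it, so both the fracture and the case leave the safety rates. The complication itself decides whether the case is counted, which is selection on outcome.

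What is at stake is the rate of surgery-related events as an absolute estimate. Femoral crack or fracture is the most frequent item in the surgery-related block of Table 4 for the sponsor's own studies (3.78%; the next is 0.94%). The fractures serious enough to prevent implantation are the ones this rule would remove.

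The analyst also has two instructions that do not agree. Sections 2.2 and 9.2.2 point to all events. Section 9.4.4 points to recipients only, and as the specific population rule it is likely to prevail.

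**Working it through.** **1. The plan's own figure.** Table 4 gives 3.78% for femoral crack or fracture, and its footnote gives 2,966 hips. The documents give no numerator. The whole number that fits is 112, since 112 / 2,966 = 3.776%, which rounds to 3.78%. Over the 2,697 subjects it would be 112 / 2,697 = 4.15%, which does not fit. The printed rate is therefore consistent with a per-hip denominator, as the footnote says.

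**2. Expected events here.** Assume the Table 4 rate applies to the 240 planned cases (Section 3.3): 0.0378 × 240 = 9.07, taken as E = 9 with N = 240.

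**3. Effect of the recipients-only rule.** Let k be the number of fractures that prevent implantation. The documents give no value for k, so it is an assumption and a range is shown.

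- All attempted cases: E / N
- Recipients only: (E − k) / (N − k)
- Fall: E / N − (E − k) / (N − k) = k(N − E) / [N(N − k)], which is positive whenever k > 0 and E < N

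| k | Events / cases | Rate | Fall (percentage points) |
|---|---|---|---|
| 0 | 9 / 240 | 3.75% | 0 |
| 1 | 8 / 239 | 3.35% | 0.40 |
| 2 | 7 / 238 | 2.94% | 0.81 |
| 3 | 6 / 237 | 2.53% | 1.22 |
| 5 | 4 / 235 | 1.70% | 2.05 |
| 9 (extreme) | 0 / 231 | 0% | 3.75 |

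The exact 95% confidence interval is 1.73% to 7.00% for 9 / 240 and 0.93% to 5.43% for 6 / 237.

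**4. Non-implantation for other reasons.** If m cases are not implanted and k of them had a fracture, the reported rate is (E − k) / (N − m). This is below E / N only when k / m exceeds E / N, here 3.75%. With m = 3 and k = 0 the rate rises to 9 / 237 = 3.80%. With m = 3 and k = 1 it falls to 8 / 237 = 3.38%. The net direction depends on why stems are abandoned, but removing a fracture case always lowers the fracture rate.

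**5. Denominators of the comparators.** Section 9.4.2 counts the control as 240 cases that received the Secur-Fit stem, and Section 9.4.4 applies the receipt condition to both groups. For operative and device-related events, the Table 4 footnote says the percentages "were calculated by dividing the number of cases with one or more reported event by the number of cases (hips) enrolled". Whether those enrolled hips included any that were not implanted is not stated.

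**The case against.** Several stronger conclusions are tempting, and the documents do not support them.

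- **That the termination rule removes the events.** Section 10.3 gives a date for a form. A fracture on the day of surgery still falls in the reporting period, and the rule deletes no adverse event. The exclusion comes from Section 9.4.4 alone.
- **That the events are lost, or are not followed up.** They stay in the database. Section 8.4 requires follow-up to resolution or stabilisation, and the adverse event form has its own resolution field with an instruction to resubmit. What remains is that a termination dated to surgery sits awkwardly with that requirement.
- **That every attempted case is dropped.** *Receive* is undefined. A stem seated and then removed in the same operation could be read as received, although the unspecified exclusion clause in Section 9.4.4 might still take it out. Withdrawal under Section 10.3 is also permissive.
- **That the rule always favours Rejuvenate.** Step 4 shows that it can raise a rate. Against Secur-Fit, both groups are conditioned on receipt, so the documents show no one-sided advantage in the Fisher comparison.
- **That Table 4 is on a different footing.** This would require knowing that *enrolled* in seven other studies included non-implanted hips. Section 3.3 of this protocol itself treats its enrolled cases as cases that will all receive the device.

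It is also fair to say that k has no source, that k = 0 gives no effect, and that 2.53% lies well inside the interval around 3.75%. These points limit the size of the problem. They do not answer it, because the safety set as written still depends on the outcome and still conflicts with the promise to tabulate all events.

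**Conclusion.** The point holds in a limited form. Section 9.4.4 defines the only safety set by receipt of the stem. On its plain reading it leaves out of the adverse event rates any case abandoned because of an intraoperative complication, although the event is collected and promised for reporting. Each such exclusion biases the absolute rate of that complication downward.

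The size cannot be determined from the documents. The illustration of 3.75% falling to between 3.35% and 2.53% rests on two assumptions: the Table 4 rate applies to this study, and 1 to 3 of 9 fractures prevent implantation. The conclusion covers absolute surgery-related rates. It does not extend to a demonstrated bias against Secur-Fit or a demonstrated mismatch with Table 4.

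**What to change.** - **Section 9.4.4:** define a safety set of all consented cases in which surgery to implant the Rejuvenate system was begun, and say what counts as begun, so that a complication before any component is inserted is classified the same way at every centre. Report the surgery-related events (the first block of Table 4) on this set, with the number attempted but not implanted stated beside each table. Keep implant-related events on recipients, and define *receive*.
- **Section 9.2.2:** refer to these sets by name. For the Fisher comparison with Secur-Fit, keep a recipients-only version of the surgery-related rates, or label the comparison as not like-for-like. Where results are set against Table 4, note that it divides by hips enrolled and that the status of non-implanted hips is not stated.
- **Sections 10.3, 8.1 and 8.4:** reconcile the date-of-surgery termination for non-implanted cases with the requirement to follow each event to resolution or stabilisation.

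The cost is one extra analysis set and a few sentences. The existing forms already hold the items needed; the sponsor should confirm that the Surgical Details and adverse event forms are submitted for non-implanted cases. The downside is that intraoperative rates may look slightly less favourable.

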10.1 Subject Recruitment and Screening

Patients will be recruited at the study centers during preoperative visits through normal referral patterns. All patients recruited for this study will have the capacity to give informed consent. Advertising for the study at each center will be at the discretion of the investigator. See

CONFIDENTIAL

Appendix D for samples of study advertisements. All handouts, brochures, advertisements, etc. must be approved by the IRB prior to the dissemination of any recruitment materials to potential subjects.

10.2 Patient Informed Consent and Guidelines

All patients for this study will be provided a consent form describing this study and providing sufficient information for them to make an informed decision about their participation. The informed consent must contain all elements required by the FDA under 21 CFR Part 50, in addition to any other elements required by state, local and institutional policies. See Appendix E for a copy of the Model Informed Patient Consent. This consent form will be submitted with the protocol for review and approval by the IRB for the study. All patients must provide written consent after having had adequate time to consider their participation in the study. The formal consent of a patient, using the IRB approved consent form, must be obtained before that patient is submitted to any protocol related procedures that are not part of normal care. Written documentation of consent must be provided on the consent's signature page in addition to a note in the patient medical records indicating the date that consent was obtained. The investigator-designated research professional obtaining the consent must also sign this consent form. The patient or their legal representative should receive a signed copy of the consent according to GCP guidelines.

The procedure for obtaining informed consent is outlined below:

- Use a current IRB approved copy of the consent form.
- Review the consent thoroughly with the patient before having them sign.
- After the patient has consented to the procedures, ensure he/she signs and dates the consent form.
- The person obtaining consent also signs and dates the signature page.
- Provide a copy of the consent to the patient.
- If required, provide the hospital with a copy of the signed consent.
- Maintain the signed original in the patient's study chart.

CONFIDENTIAL

10.3 Early Withdrawal of Subjects

When and How to Withdraw Subjects

In the event that the subject is discontinued by the investigative center prior to the final study evaluation, the subject will be notified by the center that he/she is no longer in the study and a Study Termination CRF will be completed.

The following is a list of reasons for which subjects may be withdrawn and the date of termination that should be used on the Study Termination CRF in each situation. This list is not all inclusive:

Termination Reason	Date of Termination
Death	Date of death
Investigative center termination	Date of study close-out visit
Lost to follow-up	Date Stryker termination approval given
Voluntary withdrawal	Date subject notified center of withdrawal
Revision/removal of study device	Date of revision/removal procedure
Study device not implanted	Date of surgery
Surgery not performed	Date Stryker termination approval given

At the time of study surgery it is required that the following components are implanted:

- Rejuvenate® Modular Stem
- Rejuvenate® Modular Neck
- Stryker Trident® or Tritanium™ Primary acetabular shells, with or without screw fixation, as well as Stryker Restoration® ADM acetabular shells
- Stryker alumina ceramic inserts (for use with Trident® acetabular shells) or X3® inserts
- Stryker LFIT™ CoCr heads; delta ceramic heads; or alumina ceramic heads with adapter sleeve

Revision or removal of the Rejuvenate® Modular stem/neck construct constitutes a failure and study termination for the subject.

CONFIDENTIAL

If acetabular insert or femoral head exchange is required during the study, the event is considered a reoperation and does not constitute a failure or study termination.

If acetabular shell and insert revision is required during the study, the event is considered a reoperation and does not constitute a failure or study termination.

If the subject fails to return for his/her follow-up appointments, every effort should be made to contact the subject to assess his/her health status. If after attempting to contact the subject through three documented phone calls and a certified letter, the subject still does not respond, he/she will be considered lost to follow-up. A Study Termination CRF will be completed only after notifying Stryker of the subject's status and being given approval to terminate.

In the event a subject does not have surgery, Stryker should be contacted to discuss if/when the surgery will be rescheduled. If the surgery is rescheduled more than 4 months from the date of preoperative data collection, the subject will need to be re-consented, all preoperative data will need to be re-collected and all original preoperative data will need to be removed from the database. If the surgery is not to be rescheduled or if the subject is no longer considered an appropriate study candidate, a Study Termination CRF may be completed only after notifying Stryker of the subject's status and being given approval to terminate.

When a subject completes the study according to protocol, including the final study evaluation, a Study Termination CRF will be completed.

11 Data Management

